4.1.2 Analysis Plan for Secondary Objectives

Not applicable.

4.1.3 Analysis Plan for Exploratory Objectives

Not applicable.

Date: 13-Nov-2013

4.2 Power/Sample Size

This is a descriptive study that will quantify dapagliflozin use according to selected patient characteristics. Estimates of projected dapagliflozin exposure, based on commercial forecasting, are shown in Tables 4.2-1 and 4.2-2 below.

Date: 13-Nov-2013

Table 4.2-1: Estimated Annual Number of Dapagliflozin Users in the Cegedim Databases

					Esti	mated Annual	Number of Daj	pagliflozin User	rs ¹	
	Number of Type II Diabetics, 2010 ²	% of T2DM Patients Receiving OAD Treatment ³	Estimate Annual Number of OAD Users	2012	2013	2014	2015	2016	2017	Total
France	65000	82,70%	53755 [53566 ; 53944]	-	269 [236 ; 302]	753 [697 ; 809]	1344 [1268 ; 1420]	2957 [2843 ; 3071]	3924 [3792 ; 4056]	9246 [8836 ; 9658]
UK	85000	57,20%	48620 [48246 ; 48903]	49 [35 ; 63]	146 [121 ; 170]	292 [256 ; 327]	535 [486 ; 583]	778 [718 ; 837]	924 [858 ; 988]	2723 [2474; 2968]
Italy	45000	64,50%	29025 [28777 ; 29224]	-	261 [228 ; 295]	319 [282 ; 356]	435 [391 ; 479]	784 [723 ; 843]	929 [862 ; 994]	2728 [2486 ; 2967]
Germany	70000	55,30%	38710 [38363 ; 38968]	77 [60; 95]	387 [345 ; 428]	542 [492 ; 591]	735 [676 ; 793]	968 [899 ; 1035]	1161 [1085 ; 1235]	3871 [3557; 4177]
Belgium	15000	71,90%	10785 [10658; 10893]	11 [4;17]	86 [67 ; 105]	129 [106; 153]	183 [155 ; 212]	313 [275;350]	388 [346 ; 430]	1111 [953 ; 1267]
Spain	18000	52,80%	9504 [9323 ; 9635]	-	105 [83; 126]	95 [74 ; 115]	86 [66 ; 105]	162 [134 ; 189]	200 [169 ; 230]	646 [526 ; 765]
			TOTAL	137 [99; 175]	1254 [1080; 1426]	2130 [1907; 2351]	3318 [3042;3592]	5962 [5592 ; 6325]	7526 [7112 ; 7933]	20325 [18832; 21802]

¹ Dapagliflozin uptake was estimated from AZ forecasting models; country-specific estimates were not available for Belgium. The overall EU5 update was applied to Belgium. Please see Table 4.2-2 for more information.

² Data extracted from the Diabetes Atlas, 3rd Edition, http://da3.diabetesatlas.org/index-2.html - When multiple estimates were presented, the smallest proportion was chosen.

³ OAD use alone or in combination with insulin.

Dapagliflozin Uptake - Percentage of T2D Treated Patients								
	2012	2013	2014	2015	2016	2017		
France	N/D	0.5%	1.4%	2.5%	5.5%	7.3%		
German	0.2%	1.0%	1.4%	1.9%	2.5%	3.0%		
Italy	N/D	0.9%	1.1%	1.5%	2.7%	3.2%		
Spain	N/D	1.1%	1.0%	0.9%	1.7%	2.1%		
UK	0.1%	0.3%	0.6%	1.1%	1.6%	1.9%		
UE5	0.1%	0.8%	1.2%	1.7%	2.9%	3.6%		

Table 4.2-2: Estimated Percentage Uptake of Dapagliflozin by Country¹

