1.1 Study Rationale

This drug utilization study (DUS) is being conducted as part of the BMS/AZ Dapagliflozin Risk Management Plan. Per regulatory request, this study is being conducted to describe the patients using dapagliflozin in usual clinical practice in Europe, specifically the countries reporting to our data source: Belgium, France, Germany, Italy, Spain and United Kingdom. The selection of the Cegedim Strategic Data was made because it includes data across 6 different European countries. However, an analysis of dapagliflozin patients not only required a European approval but it also requires reimbursement at the country level. As of November 2013, reimbursement was achieved in the United Kingdom and was not achieved in Belgium. In Germany, dapagliflozin was only reimbursed for 2013. Reimbursement in Italy and Spain has yet to be determined and in France, dapagliflozin is not yet reimbursed but it is expected that, should we be reimbursed, it would be only for specialist use. Since the Cegedim database includes only general practitioners, we would not expect to see any dapagliflozin users from France. Therefore, at this time, sensitivity analyses around missing data will be limited to discussions of the UK data. As this study will be on-going through 2017, country reimbursement status may change potentially resulting in more useable data from the Cegedim database.

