3.1 Overview of Study Design

This is a cross-sectional observational single-arm cohort study with descriptive data analyses among patients receiving dapagliflozin within the Cegedim Strategic Data (CSD) Longitudinal Databases (LPDs) electronic medical records (EMRs) in Europe. The assessment of combination use with loop diuretics or pioglitazone will incorporate longitudinal follow-up (See Figure 3.1-1). The study will describe the utilization pattern of dapagliflozin during the first three and a half years after marketing authorization and launch in Europe, specifically the countries reporting to this data source: Belgium, France, Germany, Italy, Spain and United Kingdom. This analysis will be repeated at 18, 30 and 42 months from the launch of dapagliflozin (T0, estimated as January 1, 2013).

The "prescription index date" for each patient included in the study will be defined as the date a patient is first prescribed dapagliflozin.

Follow-up of Subjects

The follow-up period will be used to identify concomitant use of dapagliflozin with loop diuretics or pioglitazone. Follow-up will begin on the date a patient is prescribed dapagliflozin, which will represent the beginning of follow-up (i.e., "index date"). Follow-up will continue until the discontinuation of dapagliflozin (i.e., the final day of the days' supply for the last prescription for dapagliflozin). Once a new user of dapagliflozin discontinues his/her treatment at any time (could also include an interruption in treatment), he/she will not be identified for future analyses.

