Number of patients with BMI recorded (3 years history + calc)	40,0%	62,7%	54,0%	32,1%	77,5%	24,4%
Number of patients with waist recorded (1 year history)	1,2%		0,4%			
Number of patients with Blood Pressure recorded (1 year history)	64,8%	54,5%	91,6%	28,2%	40,9%	73,4%
average records by year by patient	3,34	2,73	2,80	5,72	2,44	4,4
BIOLOGICAL EXAMS	500 800		- 20			
Number of patients with a fasting blood glucose test	29,5%	67,7%	45,6%	54,5%	44,1%	68,5%
Number of patients with a Hba1c rate	43,2%	66,4%	88,0%	77,1%	27,5%	53,6%
Number of patients with Total cholesterol	26,7%	61,2%	83,8%	57,2%	0,0%	56,4%
Number of patients with LDL	26,8%	55,4%	55,9%	54,1%	26,5%	53,1%
Number of patients with HD L	26,0%	58,3%	74,7%	52,8%	27,7%	55,9%
Number of patients with Triglycerid	27.2%	60,3%	63,9%	56,6%	41,8%	56,1%

Table 3.3.2-3: Information collected on serum creatinine and eGFR for T2DM patients in Cegedim LPDs during the course of one year (year 2012)

	FRAN	NCE	GERM	ANY	ITA	LY	SPA	IN	BELG	IUM	UK	
Number of patients in the panel	1 800	000	620 (000	700 (000	130	000	360 (000	3 200	000
T2DM patients (% of panel population)	65 000	4%	37 000 6% 42 000 6%		14 000 11%		13 000	4%	118 000	4%		
T2DM patients:												
with creatinine values recorded	20 500	32%	26 600	72%	25 000	60%	5 700	41%	7 350	57%	105 000	89%
with eGFR values recorded or calculated*	12 300	20%	19 300	52%	20 850	50%	4 200	30%	1 100	9%	93 300	79%

^{*}eGFR estimated using the Cockcroft-Gault (Appendix 5) or MDRD estimation formula (Appendix 4)

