4.3 Milestones

Descriptive statistics will be conducted 18 months after dapagliflozin has been on the market (T0 = December 2012), and annually thereafter through 3.5 years. These analyses will be shared with the CHMP. The proposed drug utilization study can be extended beyond 3.5 years if the use of dapagliflozin in the Cegedim database is less than what is currently projected; the decision to extend the study would be made in collaboration with the CHMP and would be formalized in a protocol amendment.

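### The projected total of 20,325 users is not a projection for the 42-month study: it adds years outside the window and French users the protocol does not expect, and section 4.3 names no figure to compare with.

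*Protocol*

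**What the plan says.** - **Projected size.** Section 4.2 introduces its tables with "Estimates of projected dapagliflozin exposure, based on commercial forecasting, are shown in Tables 4.2-1 and 4.2-2 below". Table 4.2-1 gives users by country for each year from 2012 to 2017, with a grand total and bracketed limits of "20325 [18832; 21802". The synopsis carries a copy without the limits.
- **Study window.** Section 3.1 says "This analysis will be repeated at 18, 30 and 42 months from the launch of dapagliflozin (T0, estimated as January 1, 2013". Section 3.2 closes the third and last dataset at 42 months. Section 4.3 dates the start differently, "T0 = December 2012), and annually thereafter through 3.5 years". Either way the last data fall around mid-2016. Section 1.1, however, describes the study as running through 2017.
- **Countries.** Section 1.1, with reimbursement status as of November 2013, says "we would not expect to see any dapagliflozin users from France". It also reports reimbursement in the UK, none in Belgium, German reimbursement for 2013 only, and no decision yet in Italy and Spain. It adds that status may change.
- **Diabetes counts.** Table 4.2-1 starts from 70,000 type 2 diabetics in Germany and 85,000 in the UK. Table 3.3.2-3 gives the counts held in the databases in 2012. Its entries for Germany and then Italy read "37 000 6% 42 000 6" (count, then percentage of the panel), and the UK count is 118,000.
- **Use of the projection.** Section 4.3 says the study "can be extended beyond 3.5 years if the use of dapagliflozin in the Cegedim database is less than what is currently projected". The decision is to be made with the CHMP and formalised in an amendment.

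**The concern.** The grand total is the headline study size, repeated in the synopsis, and a regulator would read it as what the study expects to observe. It covers a longer period than the study does. It also includes a country from which the same protocol version expects nothing.

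This matters mainly through section 4.3. The extension clause refers to the current projection, and section 4.2 holds the only projection, but no cumulative figure is given for any of the three analysis times. A reader who takes the grand total as the benchmark would find a large shortfall at month 42 whatever the true uptake, and could not tell slow uptake from a mismatch of periods.

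**Working it through.** **1. Reproducing the plan's figure.** Each cell is (type 2 diabetics) × (% on oral antidiabetics) × (annual uptake from Table 4.2-2), with the EU5 uptake used for Belgium. For Germany in 2013: 70,000 × 0.553 × 1.0% = 387. Summed over all countries and years without rounding, this gives 20,325.06, which matches the stated 20,325. The printed cells sum to 20,327 because of rounding. The multiplication is sound; the issue is what is counted.

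**2. Window.** The annual sums over countries are:

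| 2012 | 2013 | 2014 | 2015 | 2016 | 2017 |
|---|---|---|---|---|---|
| 137 | 1,254 | 2,130 | 3,318 | 5,962 | 7,526 |

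- Outside the window with no proration: 137 + 7,526 = 7,663; 7,663 / 20,325 = 38%.
- Assuming 2016 splits evenly, add 5,962 / 2 = 2,981: 7,663 + 2,981 = 10,644; 10,644 / 20,325 = 52%.
- Inside the window (January 2013 to June 2016): 1,254 + 2,130 + 3,318 + 2,981 = 9,683.
- With T0 in December 2012 (1/12 of 2012 and 5/12 of 2016): 11 + 6,702 + 2,484 ≈ 9,198. The choice of T0 changes little.

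**3. France.** Over all years, 9,246 / 20,325 = 45%. In the window: 269 + 753 + 1,344 + 2,957/2 = 3,844.5. The rest is 9,683 − 3,844.5 ≈ 5,838, made up as follows:

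| UK | Germany | Italy | Belgium | Spain |
|---|---|---|---|---|
| 1,362 | 2,148 | 1,407 | 554.5 | 367 |

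Of the German figure, only 387 belong to 2013, the one year that section 1.1 reports as reimbursed. UK plus Germany 2013 is 1,362 + 387 = 1,749.

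**4. Diabetes counts.** Germany: 70,000 / 37,000 = 1.89. UK: 85,000 / 118,000 = 0.72. The two errors run in opposite directions. With the Table 3.3.2-3 counts in all six countries, the 2012 to 2017 total is about 19,100, or 6% lower.

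In the window without France, on those counts and with half the 2016 uptake:

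- UK: 118,000 × 0.572 × 2.8% = 1,890
- Germany: 37,000 × 0.553 × 5.55% = 1,136
- Italy: 42,000 × 0.645 × 4.85% = 1,314
- Belgium: 13,000 × 0.719 × 5.15% = 481
- Spain: 14,000 × 0.528 × 3.85% = 285
- Sum: about 5,105

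UK plus Germany 2013 only: 1,890 + 37,000 × 0.553 × 1.0% = 1,890 + 205 ≈ 2,100.

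**5. Figures matched to the analyses** (current table, all countries, part-years split evenly):

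- Month 18: 1,254 + 2,130/2 = 2,319
- Month 30: 1,254 + 2,130 + 3,318/2 = 5,043
- Month 42: 9,683

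Uptake exactly on forecast would therefore stand at 9,683 / 20,325 = 48% of the grand total at month 42.

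**The case against.** Section 4.3 never names 20,325. The table gives every year by country, so a careful reader can build the month-matched figures in step 5. It would therefore go too far to infer that the extension clause cannot say anything about uptake. The clause is also permissive: extension is agreed with the CHMP, and a benchmark that is too high leans towards collecting more data. All of this stands. What remains is that the protocol leaves the choice of figure open and displays a total that does not fit the study.

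The French expectation is dated and may change, section 1.1 discloses the reimbursement position, and the synopsis lists sample size as a limitation. That also stands, so zero French users is a scenario and not a correction. Even so, the table was not brought into line with section 1.1. That section's reference to 2017 may explain the last column, but it does not rescue the total, because no dataset extends past month 42.

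Four stronger readings are tempting but not supported:

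- **A large overcount from the German base.** The UK difference offsets most of it.
- **Continuing users counted repeatedly.** This follows only if the uptake percentages are annual shares of all users, and the protocol does not say whether they are.
- **Falsely narrow limits for the total.** The stated limits are the sums of the country limits, which is wider than independent cells would give. The fair criticism is only that they carry no forecast or reimbursement uncertainty.
- **A material conflict between the two T0 dates.** They differ by about a month at most.

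**Conclusion.** The total of 20,325 is wrong as a projected size for this study. Between 38% (dates alone) and 52% (2016 split evenly) lies outside the 42-month window, and 45% is French use that section 1.1 does not expect; these two shares overlap. For the window, the protocol's own inputs give about 9,700 users with all countries, about 5,800 without France, about 5,100 without France on the database counts, and about 2,100 for the UK plus Germany 2013 on those counts. The figures assume even use within 2016 and take the annual cells at face value.

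This is a should-fix. A reader might infer that the study's results are compromised, but the documents do not support that. The analyses are descriptive, no precision target is set, all eligible users are included whatever the forecast, and no estimate depends on the total.

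**What to change.** - Restate Table 4.2-1 and its synopsis copy for T0 to month 42 only, with one T0 date and the diabetes counts of Table 3.3.2-3. The synopsis shows 5,960 for 2016 where Table 4.2-1 shows 5,962; align the two.
- Show scenarios with and without reimbursement by country, in place of a single total.
- State whether the annual figures are new or prevalent users.
- Reconcile the section 1.1 reference to 2017 with the 42-month window.
- In section 4.3, name the cumulative projection at months 18, 30 and 42, by country, as the benchmark for extension. On the current all-country figures these are about 2,319, 5,043 and 9,683, to be replaced by the restated values.

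The cost is one recalculated table, its copy, and short edits to sections 1.1, 3.1 and 4.3. The stated size becomes less favourable; no extra patients or data are needed.

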4.3 Milestones

Descriptive statistics will be conducted 18 months after dapagliflozin has been on the market (T0 = December 2012), and annually thereafter through 3.5 years. These analyses will be shared with the CHMP. The proposed drug utilization study can be extended beyond 3.5 years if the use of dapagliflozin in the Cegedim database is less than what is currently projected; the decision to extend the study would be made in collaboration with the CHMP and would be formalized in a protocol amendment.

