3.2 Study Population

The study population will be new users of dapagliflozin who meet the inclusion and exclusion criteria noted below. For research question 1-3 and 5 only, cross sectional data in new users of dapagliflozin will be used and therefore treatment interruptions are not of concern in these analyses. For research question 4, a follow-up will be performed and treatment interruptions will be dealt with as described in Section 3.1, Follow-up of Subjects.

Eligible study subjects will be selected from the study databases (described in section 3.2.1 and Figure 3.1-1). All subjects meeting inclusion and exclusion criteria and prescribed dapagliflozin within each database will be selected for inclusion for each analysis dataset:

- Patients newly prescribed dapagliflozin between T0 and 18 months meeting the inclusion criteria will be included in analysis 1 dataset.
- Patients prescribed dapagliflozin between T0 and 30 months meeting the inclusion criteria will be included in analysis 2 dataset. This second analysis dataset will include patients newly treated with dapagliflozin between 19 and 30 months and patients from analysis 1 still on treatment with dapagliflozin during the analysis 2 time period. The existing patients from analysis 1 will only contribute to the follow-up period (see section 3.1 for follow-up definition).
- Patients prescribed dapagliflozin between T0 and 42 months meeting the inclusion criteria
 will be included in analysis 3 dataset. This third cohort will include patients newly treated
 with dapagliflozin between 30 and 42 months and patients from analysis 2 still on treatment
 with dapagliflozin during the analysis 3 time period. The existing patients from analysis 2
 will only contribute to the follow-up period (see section 3.1 for follow-up definition).

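### Sections 3.1 and 4.3 of the protocol give two values for T0, the date that builds all three analysis sets, and the later one applied literally would leave out patients first prescribed in 2012.

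*Protocol*

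**What the plan says.** Section 3.1 schedules analyses at 18, 30 and 42 months from launch and dates the launch as "T0, estimated as January 1, 2013". Section 4.3 schedules the same analyses at "18 months after dapagliflozin has been on the market (T0 = December 2012), and annually thereafter through 3.5 years"; its date, "T0 = December 2012", names a month but no day.

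Section 3.2 gives T0 no date of its own but builds every dataset from it. For the first: "Patients newly prescribed dapagliflozin between T0 and 18 months meeting the inclusion criteria will be included in analysis 1 dataset". The second consists of "patients newly treated with dapagliflozin between 19 and 30 months and patients from analysis 1 still on treatment". The third is built the same way, from new users between 30 and 42 months plus patients carried over from the second. Carried-over patients contribute follow-up only. The index date "will be defined as the date a patient is first prescribed dapagliflozin" (section 3.1).

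Table 4.2-1 and the synopsis table both carry a 2012 column: 49 users in the UK, 77 in Germany and 11 in Belgium, 137 in total. France, Italy and Spain have no 2012 entry.

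**The concern.** T0 does two jobs. It opens the entry window for new users, and it fixes where the three data cuts fall. With two values, an analyst has to choose one, and the choice changes who is eligible.

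The later value is the more awkward one. A patient first prescribed in 2012 has an index date before 1 January 2013, so cannot be a new user in the first dataset. The second and third datasets admit only later new users and patients inherited from the preceding dataset, so the patient cannot enter there either. The lead sentences for those two datasets omit the word newly, but the sentences that follow, which list the composition, close that route. The protocol's own forecast nevertheless expects users in 2012, and its stated aim is to describe use over the first three and a half years from authorisation and launch.

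What is at stake is the completeness of the earliest cohort, mainly in the first report to the CHMP. Most of the 2012 forecast sits in the UK and Germany, the two databases that section 4.1.1.1 makes primary for the creatinine and eGFR analyses.

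**Working it through.** **Inputs.** T0 values from sections 3.1 and 4.3; dataset definitions from section 3.2; oral antidiabetic users and annual forecasts from Table 4.2-1; uptake percentages from Table 4.2-2.

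**1. Reproduce the 2012 forecast** (oral antidiabetic users × 2012 uptake):
- UK: 48,620 × 0.1% = 48.6 (stated 49)
- Germany: 38,710 × 0.2% = 77.4 (stated 77)
- Belgium: 10,785 × 0.1%, the EU5 rate = 10.8 (stated 11)
- Sum: 136.8 (stated 137)

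The figure reproduces, so the 2012 column follows from the uptake table and is not a misprint.

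**2. Cut dates under each T0:**

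| T0 | +18 months | +30 months | +42 months |
|---|---|---|---|
| 1 Dec 2012 | 1 Jun 2014 | 1 Jun 2015 | 1 Jun 2016 |
| 31 Dec 2012 | 30 Jun 2014 | 30 Jun 2015 | 30 Jun 2016 |
| 1 Jan 2013 | 1 Jul 2014 | 1 Jul 2015 | 1 Jul 2016 |

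The cuts differ by one day to one month, depending on the unstated December day. With even accrual within a year, a full month is 2,130/12 = 178 forecast users in 2014, 3,318/12 = 277 in 2015 and 5,962/12 = 497 in 2016. These are maxima. At the first two cuts the patients concerned simply appear in the next analysis; only the last cut changes final membership.

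**3. Share left out under the 3.1 date, if every 2012 user is lost.** Assumptions: all 137 are initiators, annual users do not overlap, and users accrue evenly within 2014 and within 2016.
- All countries to month 18: 137 / (137 + 1,254 + 2,130/2) = 137/2,456 = 5.6%
- UK to month 18: 49 / (49 + 146 + 292/2) = 49/341 = 14%
- Germany to month 18: 77 / (77 + 387 + 542/2) = 77/735 = 10%
- All countries to month 42: 137 / (137 + 1,254 + 2,130 + 3,318 + 5,962/2) = 137/9,820 = 1.4%

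**4. Difference between the two T0 values, if 2012 use is spread evenly over the year.** Only December separates 1 December 2012 from 1 January 2013: 137/12 ≈ 11 users, and 11/2,456 ≈ 0.5% to month 18. By country this is 49/12 ≈ 4 of 341 (1.2%) in the UK and 77/12 ≈ 6 of 735 (0.9%) in Germany. The other 137 − 11 = 126 or so would precede a December T0 as well and be missed under both values.

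Steps 3 and 4 answer different questions. Step 3 sizes what the 3.1 date could omit. Step 4 sizes how much of that the December date would recover if use were even across 2012. The December date recovers all 137 only if every 2012 start fell in December, on or after T0.

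**5. Window wording.** Section 3.2 uses T0 to 18 months, then 19 to 30, then 30 to 42. Read as elapsed time, there is a gap between 18 and 19. Read as numbered study months, 19 follows 18 but month 30 falls in two windows. Neither reading makes all three agree.

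**The case against.** Both sections tie T0 to the same event, the arrival of dapagliflozin on the market, and section 3.1 calls its date an estimate. If T0 simply means launch, no marketed prescription can precede it. Inclusion criterion 2 takes every patient newly prescribed during the study period, and nowhere does the protocol say that it means to exclude 2012 users. This stands: the loss arises only if the estimated date is used as a hard eligibility limit. It does not remove the contradiction, because section 3.2 needs a date and the protocol supplies two.

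The forecast is also a weak base for sizing. It gives annual users, derived from a percentage of treated patients, and not initiators. Section 1.1 has partly overtaken it: no reimbursement in Belgium, reimbursement in Germany for 2013 only, and no French users expected. This stands too. If annual users overlap, the denominators in step 3 shrink; if few of the 137 were real starts, the numerators do. The shares could therefore move either way.

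A reader might infer that the plan loses 14% of UK and 10% of German early adopters, or that the choice between the two dates is worth that much. The documents support neither. The first needs all the assumptions of step 3; the second also needs every 2012 start to fall in December.

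The window wording is a minor matter. Analyses 2 and 3 are defined cumulatively from T0, carried-over patients add follow-up only, and "This second analysis dataset will include patients newly treated with dapagliflozin between 19 and 30 months" can be read as study months. Exact cut dates could reasonably be left to the statistical analysis plan. That plan cannot settle which of two protocol dates governs without departing from one of them.

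**Conclusion.** The inconsistency is real and goes beyond a clerical slip, because T0 determines membership of all three analysis sets. Applied literally, the 3.1 date admits no patient first prescribed in 2012, against a forecast of 137 such users. The December date would also miss anything prescribed earlier in 2012.

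How many patients this affects cannot be settled from the protocol. The range runs from about 11 users separating the two dates (even use across 2012) to all 137, with the corresponding shares to month 18 being about 0.5% and about 5.6%. The effect falls mainly on the first analysis and is small by month 42, at about 1.4% even in the larger case. The study is descriptive, and nothing shows that a reported proportion would change. The point is worth correcting because the correction is so cheap; it does not threaten the study's conclusions.

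**What to change.** State one T0, as a calendar date, and use it in sections 3.1, 3.2 and 4.3. Set it no later than the first dapagliflozin prescription recorded in any participating database, so that all initiators since launch are eligible. The protocol is dated 13 November 2013, after both candidate dates, so an estimate is no longer needed. Align the entry windows in section 3.2 as T0 to month 18, after 18 to 30, and after 30 to 42.

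The cost is a wording change and one query for the earliest recorded prescription; no further data collection is needed.
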